3.2. Final Analyses

The final planned analyses (Parts A and B) will be performed after the completion of the following sequential steps:

1. All participants have completed the study as defined in the protocol (Section 4.5 End of Study Definition of the protocol): The end of the study is defined as the date of the last visit (including follow-up) of the last participant in the study (Parts A and B).
2. All required database cleaning activities have been completed and final database release (DBR) and database freeze (DBF) has been declared by Data Management. The final delivery for Part A may be generated in its own reporting area prior to the completion of Part B of the study once Data Management has declared DBF for Part A. Parts A and B final deliveries may be generated and kept in separated reporting areas.
3. All criteria for unblinding the randomization codes have been met.
4. Randomization codes have been distributed according to RandAll NG and RAMOS NG procedures.

4. ANALYSIS POPULATIONS

4.1. Analysis Populations

4.1.1. Part A and B

Population	Description	Outputs
Screened	
 All participants who were screened for eligibility 	
 Study Population (specific only)
Enrolled	
 All participants who passed screening and entered the study. Note screening failures (who never passed screening even if rescreened) and participants screened but never enrolled into the study are excluded from the Enrolled population as they did not enter the study. 	
 Study Population (Specific only)
Randomized	
 All participants who were randomly assigned to treatment in the study. This population will be based on the treatment the participant was randomized to. 	
 Study Population
Safety	
 All randomized participants who received at least one dose of study treatment. This population will be based on the treatment the participant received. 	
 Study Population (specific only) Safety PD
Pharmacokinetic	
 All participants in the Safety population who had at least 1 reportable serum PK assessment. This population will be based on the treatment the participant received. Note: Non-quantifiable [NQ] values will be considered as reportable values 	
 PK

4.1.2. Part A only

Population	Description	Outputs
Blister	
 All participants in the Safety population who had at least one blister assessment. This population will be based on the treatment the participant received. 	
 PD
Blister Pharmacokinetic	
 All participants in the Safety population who had at least 1 reportable blister PK assessment. This population will be based on the treatment the participant received. 	
 PK

CC1	
 • Note: Non-quantifiable [NQ] values will be 	
Fully treated	
 • All participants in the Safety population who received at least 80% of planned study treatment*. • This population will be identified by review of protocol deviations 	
 • PK, PD

*Part A has a single dose. Percentage of actual amount administered will be derived using the planned dose and the injected infusion volume.

4.1.3. Part B only

Population	Description	Outputs
Intent-to-Treat	
 • All randomized participants who received at least one dose of study treatment. • This population will be based on the treatment the participant was randomized to. 
Any participants who receive a treatment randomization number will be considered to have been randomized.
	
 • Efficacy
Per Protocol	
 • All participants in the ITT population who comply with the protocol. • Protocol deviations that would exclude participants from the PP population are defined in Section 4.2 (Protocol Deviations) and Appendix 1: Exclusions from Per Protocol Population*. 	
 • Efficacy (specific only)

* This population will be based on the treatment the participant was randomized to.

4.2. Protocol Deviations

Important protocol deviations (including but not limited to deviations related to study inclusion/exclusion criteria, and additionally in part B: prohibited medications, rescue medications, study medication and missing diary data) will be summarised and listed.

Important deviations which result in exclusion from the analysis population will also be summarised and listed.

Please refer to [Appendix 1](#).

Protocol deviations will be tracked by the study team throughout the conduct of the study in accordance with the Protocol Deviation Management Plan.

- Data will be reviewed prior to unblinding and freezing the database to ensure all important deviations are captured and categorised on the protocol deviations dataset.

- This dataset will be the basis for the listings of protocol deviations.

A separate listing of all inclusion/exclusion criteria deviations will also be provided. This output will be based on data as recorded on the inclusion/exclusion page of the eCRF.

5. CONSIDERATIONS FOR DATA ANALYSES AND DATA HANDLING CONVENTIONS

5.1. General

Separate outputs will be generated for both Part A and Part B.

5.2. Study Treatment Display Descriptors

In the Tables, Listings and Figures (TLF), treatment should be presented with placebo first, then in order of increasing dose by route of administration within each part.

Part A: Treatment group descriptions			
RandAll NG		Data displays for reporting	
Code	Description	Description	Order in TLF
A	0.1 mg/kg IV GSK3858279	0.1 mg/kg IV GSK3858279	2
B	0.3 mg/kg IV GSK3858279	0.3 mg/kg IV GSK3858279	3
C	1 mg/kg IV GSK3858279	1 mg/kg IV GSK3858279	4
D	3 mg/kg IV GSK3858279	3 mg/kg IV GSK3858279	5
E	10 mg/kg IV GSK3858279	10 mg/kg IV GSK3858279	6
F	SC GSK3858279	3 mg/kg SC GSK3858279	7
P	Placebo	Placebo	1

Part B: Treatment group descriptions			
RandAll NG		Data displays for reporting	
Code	Description	Description	Order in TLF
G	240 mg SC GSK3858279	240 mg SC GSK3858279	2
P	Placebo	Placebo	1

5.3. Baseline Definitions

The baseline value will be the latest pre-dose assessment with a non-missing value, including those from unscheduled visits. If time is not collected, Day 1 assessments are assumed to be taken prior to first dose and used as baseline. Replicate assessments at a timepoint will be averaged, and the mean value will be used. Unless otherwise stated, if baseline data is missing, no derivation will be performed and baseline will be set to missing.

For the average and worst knee pain intensity, the mean of the scores in index knee over 7 days prior to dosing (Day -7 to Day -1) will be considered as baseline. Baseline should be calculated only if pain scores are recorded on at least 5 days out of 7. If pain scores are not recorded on at least 5 days, the baseline will be set to missing.

For Part B of the study, the CCL17 levels (free, total) baseline value will be derived by averaging the two pre-dose measurements (i.e., average of Day-4 and Day 1).

5.4. Other Considerations for Data Analyses and Data Handling Conventions

Other considerations for data analyses and data handling conventions are outlined in the appendices

Section	Component
Section 14.3	Appendix 3: Assessment Windows
Section 14.4	Appendix 4: Study Phases and Treatment Emergent Adverse Events
Section 14.5	Appendix 5: Data Display Standards & Handling Conventions
Section 14.6	Appendix 6: Derived and Transformed Data
Section 14.7	Appendix 7: Reporting Standards for Missing Data
Section 14.8	Appendix 8: Values of Potential Clinical Importance

6. STUDY POPULATION ANALYSES

The study population analyses will be based on the Randomized population, unless otherwise specified.

Study population analyses including analyses of participants' disposition, protocol deviations, demographic characteristics, prior and concomitant medications, baseline efficacy parameters, exposure, medical history and substance use will be based on GSK Core Data Standards.

Details of the planned displays are presented in [Appendix 11](#).

7. EFFICACY ANALYSES – PART B ONLY

7.1. Co-primary Efficacy Analyses

7.1.1. Endpoint / Variables

The changes in pain in participants with OA of the knee following repeat SC administration are assessed using:

- Change from baseline in the average knee pain intensity at week 8.
- Change from baseline in the worst knee pain intensity at week 8.

7.1.2. Summary Measure

The primary summary measure will be the difference between treatments in mean change from baseline. The pain scores will be listed by participant and summarized descriptively by treatment.

7.1.3. Population of Interest

The analyses will be based on the Intent-to-Treat population, unless otherwise specified.

7.1.4. Strategy for Intercurrent (Post-Randomization) Events

There is one intercurrent event that is of interest:

1. Treatment Withdrawal (Participant discontinues the study treatment but continues to stay in the study)

No imputations would be carried out if there are missing data due to intercurrent events.

A hypothetical strategy will be used to estimate what the treatment effect would have been had the subject not experienced the intercurrent event. Data collected after the occurrence of the Intercurrent Event will be listed but not used in summary stats and stats analysis TFLs. Since the dosing interval in this study is 7 days, the date of occurrence of the treatment withdrawal intercurrent event will be defined as the date of the first missed dose of study treatment i.e. date of last dose of study treatment + 7 days. Pain scores are measured daily in the evening, therefore pain scores on or after the date of last dose of study treatment + 7 days will be considered as occurring after treatment withdrawal.

7.1.5. Statistical Analyses / Methods

7.1.5.1. Statistical Methodology Specification

Endpoint / Variables

 • Change from baseline in Average Knee Pain Intensity at Week 8 • Change from baseline in Worst Knee Pain Intensity at Week 8
Model Specification

 • A Bayesian repeated measures model will be used to fit the change from baseline from Week 1 to Week 8. • The endpoints will be assumed to follow a multivariate (MVN) normal distribution to model all repeated measurements within the same participant. • Markov-Chain-Monte-Carlo (MCMC) method will be used to estimate the posterior distributions. • A linear model for Change from Baseline at each Week (visit) will be constructed to model the within-participant covariance structures. • Terms fitted in the model will include: 
 ○ Categorical: Week (Week 1 to Week 8), Treatment (GSK3858279 and placebo), Treatment*Week Interaction, Baseline*Week Interaction ○ Continuous: Baseline ○ Repeated: Week • The prior for the Variance Covariance Matrix will follow an Inverse Wishart Distribution. • Vague priors (normal (0, var=1e6)) will be used for all other model parameters. • Set simulation size at a minimum of 10000 and 1000 burn-in iterations. The simulation size and number of burn-in iterations could be updated during the convergence check. • Refer to Appendix 6 - Bayesian Repeated Measures Model (PROC MCMC) for additional information • Refer to Appendix 3 for details on visit computation. • Refer to Appendix 9 for additional information
Model Checking & Diagnostics

 ○ Bayesian Analyses: Refer to the relevant documentation (Bayesian Statistics Best Practice at GSK – Clinical Trials using Bayesian Inference). • Refer to Appendix 9
Model Results Presentation

 • Medians and 95% credible intervals will be produced by treatment group and for the difference between treatment groups, for each of the endpoints, • The posterior distributions will be used to produce several probability statements: 
 ○ $P[True\ Difference\ (GSK3858279 - placebo) < X]$ ○ where values of X to be generated are 0, -0.6, -0.8 and -1.0 • For all tables/figures presenting results from a statistical model, a footnote including model, prior distributions, covariates and a very brief mention of intercurrent events will be added. • For all TFLs presenting efficacy endpoints, a footnote to state a range of the score for the endpoint specifying which direction of change is an improvement.

Interim Analysis 1

- A first interim analysis will occur once 20 participants reach Week 4
- The endpoint will be Change from baseline in average knee pain intensity at week 4

Interim Analysis 2

- A second interim analysis may occur once approximately 45 participants have been randomised (this estimated to happen when 28 participants reach Week 8) and will include a sample size re-estimation and a futility assessment. In addition to posterior probabilities, predictive probabilities of achieving criteria of interest at the end of the study will be estimated using a Bayesian Normal-Normal update. Vague priors for all modelling parameters will be used to compute the posterior distributions.
- Criteria of interest are:
 - $P[\text{True Difference (GSK3858279} - \text{placebo}) < X]$ where values of X to be generated are 0, -0.6, -0.8 and -1.0 and
 - Predictive probability $> X\%$
- At the interim analysis an estimate of the standard deviation of the endpoint at week 8 will be estimated from the Bayesian Repeated Measures model. Details are given in Section 14.9.1. All data available at the time of the interim will be used for this purpose
- The ratio of the Estimated SD to Predicted SD (SD=1.8) for the change from baseline at Week 8 will be used to calculate the optimal sample size as follows:

$$SS_{optimal} = \left(\frac{SD_{estimated}}{1.8} \times \sqrt{50} \right)^2$$

- The optimal sample size must be within the range [# participants randomised, 80] subjects (i.e. if the optimal calculation is >80, the SS will be capped at 80/ if the optimal calculation is <50, the SS will be capped at # participants randomised). The number of participants resulting from the SS_optimal formula must be rounded up to the next even number.

Subgroup Analyses

- No subgroup analysis is planned for the study.

Sensitivity Analyses

- Refer to Section 14.9.2 for additional information.

Supportive Analyses

- The Bayesian Repeated Measures Model will be performed on the Per Protocol Population if the Per Protocol Population comprises 50 to 90% of the ITT population

CCI

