9.2.2. Sample Size Sensitivity

Part A

A sample size sensitivity analysis has been conducted on the primary endpoint, to investigate different safety event rates. If the number of participants who completed each active dose reduces, then the true incidence rates of safety events that could not be ruled out would change. These changes are outlined below:

N Completing Cohort	Number of a particular safety event observed with GSK3858279	Upper limit of exact 95%CI indicating that a true incidence rate of x% could not be ruled out
6	2	71%
6	3	82%
	0	46%
5	1	64%
	2	78%
	0	52%
4	1	72%
	2	85%

Part B

A sample size sensitivity analysis has been conducted on the primary endpoint in Part B, to investigate a decrease or an increase in SD, current design and prediction highlighted:

N per Arm	SD	Proportion of	Proportion of	Least
		trials correctly	trials correctly	Significant
		deemed	deemed	Difference
		negative if true	negative if true	
		treatment	treatment	
		difference is 0	difference is -1	
14	1.4	80%	73%	-0.87
	1.8	67%	57%	-1.12
	2	61%	52%	-1.24
	2.2	57%	47%	-1.37
	2.4	53%	43%	-1.49
22	1.4	91%	86%	-0.69
	1.8	79%	71%	-0.91
	2	73%	65%	-1.00
	2.2	68%	59%	-1.11
	2.4	64%	54%	-1.21
25	1.4	93%	89%	-0.65
	1.8	82%	75%	-0.85
	2	77%	69%	-0.94
	2.2	72%	63%	-1.04
	2.4	67%	58%	-1.13
32	1.4	97%	94%	-0.58
	1.8	88%	83%	-0.75
	2	83%	76%	-0.83
	2.2	78%	70%	-0.91

N per Arm	SD	Proportion of	Proportion of	Least
		trials correctly	trials correctly	Significant
		deemed	deemed	Difference
		negative if true	negative if true	
		treatment	treatment	
		difference is 0	difference is -1	
	2.4	74%	65%	-1.00
40	1.4	98%	97%	-0.51
	1.8	90%	85%	-0.67
	2	88%	83%	-0.74
	2.2	84%	77%	-0.82
	2.4	80%	72%	-0.89

A sample size of up to 14 per arm (28 total) could be used to maintain the acceptable operating characteristics SD of up to 1.4, and thus provide similar operating characteristics as a trial of 50 participants with and SD of 1.8.

A sample size of up to 40 per arm (80 total) could be used to maintain the acceptable operating characteristics SD of up to 2.4, and thus provide similar operating characteristics as a trial of 50 participants with and SD of 1.8.

If the SD is 1.8 then a total of 22 (44 total) per arm completing Week 8 would still provide acceptable operating characteristics.

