9.4.5. Interim Analyses

Part A: No formal interim statistical analyses are planned. However, dose escalation meetings will occur at a relevant timepoint after each dose level; including between Parts A and B.

The decision to proceed to the next cohort, and next dose strength to be studied, will be made by the DEC based on assessment of safety and serum GSK3858279 pharmacokinetic data obtained in all participants at the prior dose level. Individual safety data (AEs, laboratory safety tests, ECGs and vital signs) will be reviewed. In addition, un-blinded preliminary PD data may be reviewed by the DEC during the study; where the GSK biology lead will join the DEC in these discussions. Once sufficient safety, PK and target engagement data is collected from the top IV dose and SC cohorts, a data review will take place and a decision to proceed with Part B of the study may be made. Further details are included in the DEP.

Unblinded data from Part A may be reported out in full following the last subject last visit in this part of the study and prior to the conclusion of Part B.

Part B: An interim analysis will occur once approximately 20 participants have completed the Week 4 assessment. A second interim analysis and an unblinded sample size re-estimation may occur prior to enrolling the 50th participant, where the sample size could be decreased to a minimum of 20 or increased to a maximum of 80 participants.

Additional interim analyses may occur in order to inform internal decision making. Full details of all interim analyses will be prospectively outlined in the interim analyses charter.

At the interim analyses, treatment group level, efficacy, safety, PK, TE, rescue medication and ADA data may be reviewed by a list of people included in the IA charter, including the Project Leader and Independent Internal Review Board and internal governance boards as required. Individual participant data may be reviewed at the request of the project leader, but subject identification numbers will be removed to maintain the blind.

If there are interactions with regulatory agencies, any interim data presented will be at the treatment group level unless individual participant data is requested. Unblinded safety information may be presented at an individual level

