Part B Design Features	
 In Part B, the total duration of the study (from 1st screening visit until final follow-up) for each participant will be up to 182 days (inclusive of a screening period of a maximum of 42 days). Approximately 50 (up to a maximum of 80) participants with OA will be randomly assigned to GSK3858279 or placebo in a 1:1 ratio. Each participant will receive weekly SC doses of either 240 mg GSK3858279 or placebo for 8 weeks. Close in-stream safety review (AEs, clinical laboratory, vital signs, cardiac monitoring) is planned throughout for all participants (see Safety Management Plan). An early detailed review of safety, PK, TE and ADA data following administration of repeat doses is intended for the first 8 participants (4 randomized to active treatment) when the 8th participant completes the Week 4 assessment. A second detailed review of safety, PK, TE and ADA data is intended for the first 20 participants (10 randomized to active treatment) when the 20th participant completes the Week 4 assessment. An interim analysis for futility will occur once approximately 20 participants have completed the Week 4 assessment. A second interim analysis for an unblinded sample size re-estimation, including a futility assessment, may occur prior to enrolling the 50th participant, where the sample size could be decreased to a minimum of 20 or increased to a maximum of 80 participants enrolled if the observed SD of Change from baseline in the average knee pain intensity at week 8 is smaller or greater than 1.8 respectively. Sample size increase may also occur to account for participants who discontinue the treatment or study prior to Week 8. See Section 7.1.5.1 for more details Additional interim analyses may occur for internal decision making and/or interaction with regulatory agencies as appropriate. 																

Study Design							
Part B Time & Events	
 Refer to Appendix 2 						
Part B Treatment sequences	
 Participants will be assigned to either GSK3858279 or placebo in a 1:1 ratio, where the intervention codes are as follows: 
  
 Intervention code	Intervention Description	
   
 G	240 mg SC GSK3858279	
 
 P	Placebo	
  
	Intervention code	Intervention Description	G	240 mg SC GSK3858279	P	Placebo

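### SAP 7.1.5.1 gives two different lower triggers for the re-estimated sample size, and the minimum of 20 attached to this step cannot be reached under the SAP's own timing and floor

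*SAP*

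**What the plan says.** SAP 7.1.5.1, under Interim Analysis 2, sets the timing: "A second interim analysis may occur once approximately 45 participants have been randomised", which it expects to coincide with 28 participants reaching Week 8. The formula is N = (estimated SD / 1.8 × √50)². Three statements then govern its result:

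- The bound: "The optimal sample size must be within the range [# participants randomised, 80] subjects".
- The bracket explaining the bound. Above 80, N becomes 80. At the lower end, "if the optimal calculation is <50, the SS will be capped at # participants randomised".
- The rounding: "The number of participants resulting from the SS_optimal formula must be rounded up to the next even number".

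Protocol 9.4.5 describes the same step as one "where the sample size could be decreased to a minimum of 20 or increased to a maximum of 80 participants". Protocol 1.1 and SAP 2.3 and 3.1 agree, and Protocol 4.2 and 9.2.1 repeat 20 as the minimum for Part B. Protocol 9.2.2 adds: "A sample size of up to 14 per arm (28 total) could be used to maintain the acceptable operating characteristics", for an SD of up to 1.4.

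On dropout, SAP 2.3 says "Sample size increase may also occur to account for participants who discontinue the treatment or study prior to Week 8" and refers the reader to 7.1.5.1 for details. The formula there contains only the SD.

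**The concern.** The bracket is introduced as a restatement of the bound, but it moves the lower trigger. Under the bound, a formula value of 48 with 45 randomised is admissible and needs no adjustment. Under the bracket, the same 48 is replaced by 45. The upper end has no such problem.

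The look is unblinded. A rule that fixes the final sample size should have one reading before treatment results are seen, including the order of rounding and capping.

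The second issue is the stated range. A reader of the protocol would take it that a small SD at this step could bring the trial down towards 20. Under the SAP's timing and floor it cannot.

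**Working it through.** **Inputs.** Planned N 50 (25 per arm), SD 1.8, positive if the posterior probability of any benefit is at least 90%, negative if the probability that the difference is worse than −1.0 is at least 85% (Protocol 9.2.1). Formula, bound, bracket, rounding and timing come from SAP 7.1.5.1.

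**Reproducing the plan's figures.** Use a normal approximation with a vague prior and SE = SD × √(2/n per arm). The positive rate at a true difference of −1 is Φ(1/SE − 1.2816). The negative rate at a true difference of 0 is Φ(1/SE − 1.0364). With n = 25 and SD 1.8, SE = 0.509 and 1/SE = 1.964, giving 75.3% positive and 82.3% negative. The protocol states 75% and 82%.

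**The two lower triggers.** N = 50 × (SD/1.8)², with 45 randomised:

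| Estimated SD | Formula N | Rounded to even | Bound alone | Bracket, tested before rounding | Bracket, tested after rounding |
|---|---|---|---|---|---|
| 1.40 | 30.2 | 32 | 45 | 45 | 45 |
| 1.65 | 42.0 | 44 | 45 | 45 | 45 |
| 1.72 | 45.7 | 46 | 46 | 45 | 45 |
| 1.75 | 47.3 | 48 | 48 | 45 | 45 |
| 1.78 | 48.9 | 50 | 50 | 45 | 50 |
| 1.80 | 50.0 | 50 | 50 | 50 | 50 |
| 1.90 | 55.7 | 56 | 56 | 56 | 56 |
| 2.30 | 81.6 | 82 | 80 | 80 | 80 |

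The unrounded formula reaches 45 at SD = 1.8 × √(45/50) = 1.708, so the readings differ from about 1.71 to just under 1.80. If rounding comes first, the window starts slightly lower, at about 1.69, because values just above 44 round up to 46. The largest gap is 50 − 45 = 5.

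**How often.** Treat the SD estimate as chi-square based with 26 degrees of freedom (28 participants at Week 8, two arms) and a true SD of 1.8. The estimate then falls between 1.708 and 1.80 with probability 0.147. For true SDs of 1.6, 1.7 and 2.0 the probability is 0.119, 0.146 and 0.100. This is an approximation: the SAP's own estimator, in 14.9.1, uses a model-based SE and an effective sample size.

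**What it costs.** At SD 1.8 (45 is entered as 22.5 per arm):

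| Total N | Positive at −1 | Negative at 0 |
|---|---|---|
| 50 | 75.3% | 82.3% |
| 45 | 72.0% | 79.6% |
| 44 | 71.3% | 79.0% |

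The last row matches Protocol 9.2.2, which lists 79% and 71% for 22 per arm and calls 44 participants completing Week 8 acceptable at this SD. (The second percentage is headed there as a negative rate, but its 75% at 25 per arm is the positive rate of 9.2.1.)

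**The minimum of 20.** The formula returns 20 at SD = 1.8 × √(20/50) = 1.138. With 45 randomised, both clauses then return 45. At SD 1.4, the case for which Protocol 9.2.2 mentions 28, the formula gives 30.2, rounded to 32, and the rule again returns 45. The lowest N this step can give is the number already randomised.

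**The case against.** The strongest reply is that the bound is only a limit, the bracket is the operational rule, and the bracket's output always respects the limit. A programmer who follows the bracket gets one number, apart from the rounding question. That is fair as far as it goes. But it means that the SAP computes an optimal N and then discards it whenever it falls between the number randomised and 50, with a jump at SD 1.8 that nothing in the text explains. If that policy is intended, the bound does not describe it.

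The size of the problem is also open to challenge, and here the reply largely stands. The readings agree about 85% of the time when the true SD is 1.8. The gap of 5 is the maximum; at SD 1.72 it is 1. On the SAP's own timing, 45 − 28 = 17 participants are randomised in 8 weeks, about 2.1 per week, so 45 becomes 50 in about 2.4 weeks. No recruitment pause is stated, and if 50 are randomised by the decision the conflict disappears. The rates at 45 are about those the protocol already accepts for 44. One reservation remains: 44 counts completers. With 45 randomised, two without Week 8 data fall below it; with 50, it takes seven.

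On the minimum, 20 can be read as an outer limit. The protocol requires only that the look come before the 50th enrolment, the SAP timing is approximate, and a futility stop could end the trial lower. All true, but neither a futility stop nor an earlier look is the re-estimation as the SAP schedules it.

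On dropout, a reader might infer that discontinuations can never change N. The documents do not support that: SAP 2.3 is permissive, and both documents place further interim detail in a charter that is not available here. What can be said is that the cross-reference leads to a section with no dropout term.

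**Conclusion.** The inconsistency is real and its effect is small. The lower trigger in SAP 7.1.5.1 has two readings that differ when the estimated SD is about 1.71 to just under 1.80 at 45 randomised. That is roughly a 15% event if the true SD is 1.8, on the chi-square approximation with 26 degrees of freedom. The consequence is at most 5 participants, moving the positive and negative rates from 75.3% and 82.3% to 72.0% and 79.6% at SD 1.8. There is no consequence once 50 are randomised.

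The minimum of 20 is not attainable by this re-estimation under the SAP's timing and floor; only a futility stop or an earlier look could end lower.

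A reader might go further and conclude that the trial's size is undetermined in its most likely region, or that the design loses acceptable performance. Neither follows: the readings agree most of the time, and the lower figure stays about the level that Protocol 9.2.2 accepts. Nor is the 28-participant sentence in 9.2.2 a commitment about this interim; it is a sensitivity statement.

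**What to change.** In SAP 7.1.5.1, replace the bracket with N = min(80, max(number randomised, formula N rounded up to even)), and state that rounding precedes the caps. In Protocol 1.1 and 9.4.5 and SAP 2.3 and 3.1, restate the minimum for this step as the number already randomised (about 45), and note that a lower total can arise only from a futility stop.

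For dropout, choose one of two options:

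- Delete the SAP 2.3 sentence that points to 7.1.5.1.
- Divide the formula N by the proportion with usable Week 8 data among participants who have reached, or would by then have reached, their Week 8 date, still capped at 80.

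The denominator matters. If all 45 randomised were counted while only 28 had reached Week 8, the calculation at SD 1.8 would be 50/(28/45) = 80.4 and N would go to the cap of 80 with no dropout at all.

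The cost is wording in both documents. The single rule adds at most 5 participants compared with the bracket, all within the planned 50. A dropout adjustment could add more, up to the existing cap of 80.
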